2.1. Objective

The MERIT Trial was designed to find out which intravitreal therapy offers the best balance of effectiveness and tolerability in treating persistent or recurrent uveitic macular edema in eyes with controlled uveitis, specifically by comparing the relative efficacy and safety of intravitreal ranibizumab (Lucentis®) and intravitreal methotrexate to intravitreal dexamethasone implant (Ozurdex®) for the treatment of persistent /recurrent uveitic macular edema.

2.2. Hypotheses

- (1) Intravitreal injections of methotrexate will have greater efficacy than intravitreal injections of the dexamethasone pellet as a treatment for uveitic macular edema persisting or recurring after treatment with an intravitreal corticosteroid injection.
- (2) Intravitreal injections of ranibizumab will have greater efficacy than intravitreal injections of the dexamethasone pellet as a treatment for uveitic macular edema persisting or recurring after treatment with an intravitreal corticosteroid injection.

3. Design

[figure not shown]
3.1. Type of study

- Randomized, three-arm, parallel design, randomized comparative effectiveness trial
- Randomization stratified by presence or absence of concomitant systemic corticosteroid and/or immunosuppressive therapy for any indication
- Unit of randomization is patient, not eye; if both eyes meet eligibility criteria, both receive same treatment
- Allocation ratio (1:1:1)
- Multicenter
- Fixed sample size, 240 (80 per treatment group)
- Anniversary close-out at the 6-month clinic visit
- Reading center graders and visual acuity examiners will be masked to treatment
- Treating physicians and patients will be unmasked (the intravitreal therapies are different in appearance and have potentially different injection schedules)

3.2. Treatment arms

- Ozurdex (0.7 mg dexamethasone pellet) delivered via intravitreal injection
- Methotrexate 400 µg in 0.1 mL via intravitreal injection
- Ranibizumab (Lucentis) 0.5 mg in 0.05 mL via intravitreal injection

3.3. Trial schema

Intravitreal dexamethasone arm

- * Eligible eye(s) treated M01⁺
- ‖ Retreatment required at M03 if retreatment criteria met
- Δ Retreatment permitted at M04 or later if retreatment criteria met

Intravitreal methotrexate arm

- † Eligible eye(s) treated M01⁺
- †† Retreatment required at M02, M03 if retreatment criteria met
- Δ Retreatment permitted at M04 and later if retreatment criteria met

Intravitreal ranibizumab arm

- § Eligible eye(s) treated at M01⁺, M02 and M03
- Δ Retreatment permitted at M04 and later if retreatment criteria met

Retreatment criteria

- 1) Central subfield thickness greater than 1.1X upper limit of normal (330 µm for Zeiss and Topcon SD OCT and 352 µm for Heidelberg OCT) and/or cystoid space(s) within 1 mm central subfield.
- 2) IOP of <25 mm Hg (treatment with ≤3 IOP-lowering agents permitted)

⁺ IOP criteria for initial injection of study treatment in eligible eye(s) is ≤21 mm Hg with ≤3 IOP-lowering agents

Minimum time between injections

- Intravitreal dexamethasone: minimum *target* 8 weeks after last injection but re-injection *permitted* as early as 51 days after last injection;
- Intravitreal methotrexate: minimum *target* 4 weeks after last injection but re-injection *permitted* as early as 23 days after last injection
- Intravitreal ranibizumab: minimum *target* 4 weeks after last injection but re-injection *permitted* as early as 23 days after last injection

3.4. Primary outcome

The primary outcome is the percent change in central subfield thickness from the baseline OCT measurement at the 12-week visit. The assessment of OCT outcomes will be performed by masked readers. The 12-week visit was chosen as the time to assess the primary outcome because the ranibizumab treatment arm specifies injections at baseline (i.e., post-randomization), 4 weeks and 8 weeks in all participants, and because the peak benefit for the dexamethasone pellet appears to be at the 8 to 12 weeks.

3.5. Secondary outcomes

- Rates of IOP elevation of ≥ 24 mm Hg, ≥ 30 mm Hg, and ≥ 10 mm Hg from baseline during the 24 weeks of follow-up
- Percent change in macular thickness as measured by OCT over the 24 weeks of follow-up
- Proportion of eyes with macular edema events over the 24 weeks of follow-up
 - $\geq 20\%$ reduction in macular thickness (or normalization of macular thickness even if there is $<20\%$ reduction)
 - "Resolution", defined as normalization of the macular thickness, i.e., <260 μm on the standard scale Worsening defined as a 20% increase in macular thickness from the lowest value after an injection
 - "Recurrence" defined as $>20\%$ increase in the central subfield measurement on OCT to an abnormal value in an eye that previously had resolution of ME
- Mean change in BCVA over the 24 weeks of follow-up.
Best-corrected visual acuity score will be measured at every study visit under standardized lighting conditions by certified study examiners masked to study treatment using logarithmic (ETDRS) visual acuity charts, according to the method described by Ferris, et al.¹²⁷
- Safety outcomes including elevated IOP (>30 mm Hg thresholds); vitreous hemorrhage; retinal tear/detachment; endophthalmitis; severe vision loss (≥ 15 Early Treatment Diabetic Retinopathy Study [ETDRS] letters) during the 24 weeks of follow-up.

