3.5 Secondary outcomes

Revised secondary outcomes to reflect the outcomes planned for inclusion in the manuscript reporting the primary results

- Added rate of IOP elevation of ≥ 24 mm Hg and ≥ 30 mm Hg; removed rate of IOP elevation of >21 mm Hg

- For resolution of macular edema, changed the criteria for normalization of macular thickness from “to within +2 standard deviations of the normative mean for the OCT machine used” to “<260 um on the standard scale”
- Removed the following outcomes and associated references
 - Inflammation graded using semi-quantitative scales
 - New onset posterior subcapsular (PSC) cataract or progression of pre-existing PSC (using the Age-Related Eye Disease Study [AREDS] scheme
 - Cost effectiveness
 - Visual function related quality of life

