3.8 Data collection table

Deleted the following:

- Fundus reflex images (for phakic eyes) at M01 and M07
- Fluorescein angiogram at M01

Abstract

Macular edema (ME) is the most common structural complication and cause of visual impairment and legal blindness in uveitis patients. Traditional approaches to the treatment of uveitic ME have included the use of regional corticosteroid therapy, delivered periocularly, including posterior sub-Tenon's and orbital floor injections, or via the intravitreal route. While corticosteroid injections may reduce ME and improve vision, the effect is often variable with a limited duration. Persistent or recurrent macular edema is a common occurrence and often requires repeated intravitreal injections of corticosteroids, which expose eyes to a significant risk of increased intraocular pressure ocular and cataract development. The often refractory nature of uveitic ME and its impact on visual function underscores the need to identify effective alternative medical therapeutic options. Recent pilot studies have shown intravitreal methotrexate (MTX) and intravitreal ranibizumab (Lucentis[®], Genentech Inc., San Francisco, CA) to be promising treatments for uveitic ME, and intravitreal dexamethasone implant (Ozurdex[®], Allergan, Irvine, CA) has recently been approved for uveitic ME in patients with non-infectious uveitis. In addition to being effective, intravitreal MTX and ranibizumab potentially may have less ocular side effects than corticosteroids, particularly less IOP elevation. However, the relative efficacy of these treatments is unknown. The Macular Edema Ranibizumab v. Intravitreal anti-inflammatory Therapy (MERIT) Trial will compare the relative efficacy and safety of intravitreal methotrexate, ranibizumab, and dexamethasone implant for persistent or recurrent macular edema. MERIT is a parallel design (1:1:1), randomized comparative effectiveness trial with an anniversary close-out at the 6-month clinic visit. The primary outcome is percent change in central subfield thickness from the baseline OCT measurement to the 12-week visit. Secondary outcomes are: improvement of macular edema based upon the MUST-accepted definition of ME improvement; resolution of macular edema based on the MUST-accepted definition of ME resolution (i.e., return to normative mean +/-2 standard deviations of the central subfield measurement); improvement in best corrected visual acuity; adverse events (i.e., cataract and IOP elevation); cost-effectiveness.

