In an effort to address the limited duration of action of intravitreal triamcinolone, sustained release implants have been developed and approved by the FDA, including the dexamethasone implant, Ozurdex. This implant is a copolymer containing dexamethasone, lactic acid and glycolic acid, which releases dexamethasone over a six month period as it degrades slowly into carbon dioxide and water. It is administered as an office based injection into the vitreous cavity.⁸¹⁻⁸⁷ The safety and efficacy of a single intravitreal injection of two dexamethasone pellet doses (0.7mg and 0.35mg) was reported from the HURON study, a 26-week, phase III, prospective, multicenter, masked, sham injection-controlled, randomized clinical trial among 229 patients with noninfectious intermediate or posterior uveitis.⁸⁸ Patients were randomized 1:1:1 to receive the higher-dose (0.7mg) pellet, the lower-dose (0.35mg) pellet, or a sham injection. The primary outcome was control of vitreous inflammation. Although both implant doses were shown to be effective in controlling vitreous inflammation and in improving visual acuity, the higher dose implant proved to have a longer duration of action without a significant increase in untoward ocular side effects and is the dose currently in clinical use. At 8 weeks after injections, 43% of treated eyes versus 7% in the sham group had at least a 15-letter improvement from baseline best corrected visual acuity, and the proportion of eyes achieving this level of improvement was 2- to 6-fold greater in the dexamethasone pellet groups as compared to the sham group at each visit throughout the study period. Evaluation of macular edema was performed with time-domain OCT, and there was a significant decrease in the mean macular thickness for both treatment groups (-99 μ m for the higher-dose group and -91 μ m for the lower-dose group) when compared to the sham-treated group (-12 μ m, $P < 0.004$) at the eight-week visit. The proportion of eyes with improvement and/or resolution of the macular edema were not reported. The percentage of eyes with IOP ≥ 25 mm Hg peaked at 7.1% for the higher-dose implant group, 8.7% for the lower-dose implant group, and 4.2% for the sham-treated group. At 26 weeks, there was no statistically significant difference in the occurrence of cataract among groups (15% higher-dose, 12% lower-dose, and 7% sham-treated) with no patient requiring cataract surgery. However, patients with a history of an elevated IOP related to topical or regional injection corticosteroids were excluded from this study, so the comparative rate of IOP elevation vs. intravitreal triamcinolone is uncertain. Subsequent small, retrospective case series

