1.8. Rationale for trial

Although regional corticosteroid injections reduce macular edema and improve vision in many patients, the effect is variable, and up to 50% of eyes with uveitic macular edema have persistent edema, despite control of the inflammation.¹⁶ Furthermore, the ocular side effects, of increased IOP and cataract formation, have been reported in a substantial proportion of patients treated with regional corticosteroid injections, and an increase in the risk of such side effects (e.g. cataract formation) may increase with multiple injections.^{73, 78, 125} Hence there is a need for alternative agents with a different side effect profile (or lower rates of side effects).

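### The abstract and section 3.5 disagree on cataract, cost-effectiveness and resolution, and cataract is left to adverse event reports whose required window can close at different times by arm

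*Combined protocol and SAP*

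**What the plan says.** **Abstract (current text).** The secondary outcomes include "adverse events (i.e., cataract and IOP elevation); cost-effectiveness". Resolution of macular edema means a central subfield measurement back within two standard deviations of the normative mean.

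**Section 3.5 (current text).** Resolution is <260 µm on the standard scale. Several IOP thresholds are listed. Besides elevated IOP, the safety item names "vitreous hemorrhage; retinal tear/detachment; endophthalmitis; severe vision loss". There is no cataract outcome and no cost-effectiveness outcome.

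**Objective and rationale.** Section 2.1 asks "which intravitreal therapy offers the best balance of effectiveness and tolerability". Section 1.8 motivates the search for other drugs with the statement that "the ocular side effects, of increased IOP and cataract formation, have been reported in a substantial proportion of patients" given regional corticosteroid injections.

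**Revision history, version 1.6.** Among the outcomes removed from 3.5 is "New onset posterior subcapsular (PSC) cataract or progression of pre-existing PSC", along with cost effectiveness. The same revision changed the resolution criterion to <260 µm. The stated reason is to match the outcomes planned for the primary results paper. Version 1.8 then deleted the lens images for phakic eyes.

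**Adverse events.** Section 3.8 schedules an ophthalmic exam and adverse event monitoring at every visit from M01 to M07 (week 24). Section 7.1 lists cataract as a dexamethasone effect. Section 8.3.1 closes required reporting 30 days after the last study treatment, or at study discontinuation if earlier. After that, only serious events attributed to study treatment are to be reported. Section 9.2 compares adverse event rates with a Negative Binomial model.

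**The concern.** Two pieces of current text give different outcome lists. A reader of the abstract would believe that cataract is a compared outcome; a reader of 3.5 would not. The removal was deliberate, but section 2.1 was not narrowed to match, and section 1.8 still presents cataract as one of the two steroid harms that justify the trial.

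That leaves general adverse event reporting to carry cataract. The plan does not say what counts as new or worsened cataract, and it does not restrict the comparison to eyes that still have a natural lens. The required reporting window also depends on when a participant was last injected, and the injection schedule differs by arm. A comparison of recorded cataracts could therefore reflect how long each arm was under required reporting as well as what the drugs do.

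**Working it through.** **1. Abstract against section 3.5**

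| Item | Abstract | Section 3.5 | Version 1.6 change |
|---|---|---|---|
| Cataract | Secondary adverse outcome | Not named | Graded cataract outcome removed |
| Cost-effectiveness | Secondary outcome | Absent | Removed |
| Resolution | Normative mean ±2 SD | <260 µm | Changed to <260 µm |

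All three mismatches trace to one revision that reached 3.5 but not the abstract.

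**2. What the adverse event route provides.** Cataract can be recorded at any visit and enter the rate comparison in 9.2. Four features weaken it:
- No cataract definition or phakic denominator is given in 3.5, section 8 or 9.2.
- Section 8.2.1 describes safety assessment in terms of events considered related to treatment, and treating physicians are unmasked (3.1).
- The special-interest list in 8.4.10 is for ranibizumab and names only traumatic cataract.
- The reporting window in 8.3.1 depends on the last injection (step 3).

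**3. Reporting window.** Inputs: visit weeks (3.8), injection schedule (4.2.1), 30-day rule (8.3.1). Follow-up is 24 × 7 = 168 days. Window end = day of last study injection + 30, taking the first injection as day 0.
- Dexamethasone, M01 only: 0 + 30 = day 30; 30/168 = 18% of follow-up.
- Dexamethasone, M01 and week 8: 56 + 30 = day 86; 86/168 = 51%.
- Ranibizumab, M01, week 4 and week 8 as scheduled: 56 + 30 = day 86 at the earliest.
- Methotrexate: day 30 if treated only at M01, 28 + 30 = day 58 if last treated at week 4, day 86 if at week 8.

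In any arm, an injection at M04 or later extends the window. The first injection may also fall up to 10 days after randomization. None of these windows is guaranteed to reach day 168, although 3.8 schedules monitoring to that point.

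**4. Precision of a cataract comparison.** The plan has no figure for cataract. Its sizing figure reproduces: with ln 0.75 − ln 0.62 = 0.1904, SD 0.33, 79 eyes per arm and two-sided alpha 0.025, power is 91.7% (normal) or 91.2% (noncentral t), against 91% stated. That figure concerns thickness only.

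For cataract, section 1.6 reports 26-week rates in the sham-controlled trial of the dexamethasone implant: "15% higher-dose, 12% lower-dose, and 7% sham-treated". Illustration, assuming 15% on dexamethasone, 7% (the sham rate) on a comparator and one eye per person:

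power = Φ{[0.08 − 1.96·√(2·0.11·0.89/n)] / √[(0.15·0.85 + 0.07·0.93)/n]}

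| Phakic fraction (assumed) | Eyes per arm, n | Power, alpha 0.05 |
|---|---|---|
| 100% | 80 | 36% |
| 70% | 56 | 27% |
| 50% | 40 | 21% |
| 30% | 24 | 14% |

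At alpha 0.025, power with 80 per arm is 26%. About 239 per arm would be needed for 80% power at alpha 0.05. The 95% interval for the difference has half-width 1.96 × √(0.1926/80) = 9.6 points with 80 eyes per arm and 1.96 × √(0.1926/40) = 13.6 points with 40, against an assumed difference of 8 points.

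**The case against.** The strongest reply is that the change to 3.5 was intended and logged, so the abstract is merely out of date and the choice of secondary outcomes belongs to the sponsor. The safety list in 3.5 is also worded as open-ended, exams and adverse event monitoring take place at every visit, 7.1 recognizes cataract as a dexamethasone effect, and 9.2 compares event rates. Section 1.6 adds that the 15% versus 7% difference was not statistically significant and that no patient needed cataract surgery by 26 weeks. Reporting details sit in a Manual of Procedures that is not part of these documents.

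Much of this stands, and it rules out several stronger readings:

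- A reader might infer that nothing in the trial measures cataract. The documents do not support that. What is missing is a defined outcome with a denominator and a common observation period.
- A reader might infer that including eyes without a natural lens in the event model biases the comparison toward dexamethasone. It does not, on the usual log link. If a fraction f is phakic in both arms, which randomization gives in expectation, the ratio is (f × 15)/(f × 7) = 2.1 whatever f is. Only the absolute difference shrinks.
- A reader might size the problem from the triamcinolone figures in 1.6. Triamcinolone is not a study drug, and 1.6 says the dexamethasone pellet may have lower side-effect rates.
- A reader might infer that the trial will formally name a winner without counting cataract. Neither 9.2 nor section 10 contains a benefit-harm rule; the confirmatory analysis is thickness at 12 weeks.

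The reply does not answer the contradiction in current text, the unchanged objective and rationale, or the conflict between 8.3.1 and 3.8.

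**Conclusion.** The point holds as an inconsistency and as a gap in how cataract is ascertained. Three items in the abstract contradict 3.5, and the abstract is the stale text. Cataract, a harm the trial cites as a reason for being done, is left to adverse event reports without a definition or phakic denominator. The required window can close at about day 30 in the dexamethasone arm, against about day 86 or later for ranibizumab given as scheduled.

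Differential ascertainment is possible, not shown. Its size depends on how many participants are retreated and on whether sites keep reporting to week 24 as 3.8 implies; the documents settle neither. The precision figures assume the cited 15% and 7% carry over, that the sham rate stands in for the comparator, and a phakic fraction the protocol does not give. Section 1.6 also does not say whether those percentages are of phakic eyes or of all patients.

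The primary analysis and sample size are unaffected. This is a worthwhile, inexpensive improvement to the tolerability evidence.

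**What to change.** 1. Add to the safety outcomes in 3.5: new or worsened cataract on the scheduled ophthalmic exam, and cataract surgery, in study eyes phakic at M01, ascertained to week 24 in all arms. Report by assigned arm as descriptive estimates with confidence intervals.
2. State in 3.8 that lens status is recorded at M01 and at follow-up.
3. Reconcile the reporting window in 8.3.1 with adverse event monitoring at every visit in 3.8.
4. State with the objective that the tolerability conclusion applies to 24 weeks.
5. Make the abstract's outcome list (cataract, cost-effectiveness) and resolution definition match 3.5.
6. If BCVA is examined by lens status, use baseline status only. Cataract progression occurs after randomization and can be affected by treatment, so selecting eyes on it would break the randomized comparison.

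**Cost.** Wording changes, possibly one item on the exam form, and one descriptive table. Exams already occur at every visit, and no lens photographs or graded readings are needed. Whether current forms capture lens status cannot be seen from these documents.

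**Downside.** The treating physicians are unmasked and may look harder for cataract after a steroid implant. Surgery is a firmer event but may be rare or absent by week 24. With power of about 36% or less, the outcome can describe the harm but cannot establish or exclude a difference.

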immunosuppression, particularly juvenile idiopathic arthritis-associated chronic anterior uveitis. Intravitreal methotrexate has been used successfully in the treatment of primary intraocular lymphoma without the occurrence of substantial adverse ocular effects.^{94, 95} A dose of 400µg/0.1 mL is well tolerated by the retinal tissue and remains in a therapeutic concentration for 48-72 hours.⁹⁶ Several case series have suggested efficacy for intravitreal injections of methotrexate (400µg/0.1 mL) for the treatment of chronic intermediate uveitis and posterior uveitis and for inflammatory macular edema.⁹⁷⁻¹⁰⁰ A six-month pilot study of patients with active intermediate, posterior, or panuveitis from Moorfields Eye Hospital examined the effect of a single intravitreal injection of methotrexate on visual acuity and macular edema.⁹⁸ Overall, 87% (13/15) of patients responded with significantly improved visual acuity, significantly reduced macular thickness on OCT, and significantly reduced ocular inflammatory scores. The onset of action appeared to be within one week of administration with a mean duration of effect of four months. Visual improvements were similar to those seen with previous injections of intravitreal triamcinolone. Patients who underwent a second injection had a similar response. No patients had an increase in IOP. The only evident treatment related side effect was corneal epitheliopathy in one patient, occurring two months following the initial injection. These data suggest that intravitreal methotrexate may be effective for the treatment of uveitis and of uveitic macular edema and that it may have lower rates of the ocular side effects of elevated IOP and cataract. However, the relative merits of this approach vs. repeat injections of intravitreal triamcinolone are unknown.

Ranibizumab

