7.1. Intravitreal dexamethasone

- Commonly reported events related to the drug
 - Elevated intraocular pressure (IOP) which may require medication to lower
- Less frequently reported events related to the drug
 - Short-term visual disturbances
 - Headache
 - Cataract development
 - Elevated intraocular pressure (IOP) which may require surgery to control
 - In eyes with non-intact posterior capsule, implant migration to anterior chamber
 - Patients with diabetes could experience a transient elevation in blood glucose
- Rare and serious events related to the drug
 - Perforation of the globe where there is thinning of the cornea or sclera
- *Possible side effects and complications related to intravitreal injections are listed in section 7.4*

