7.2. Intravitreal methotrexate

- Commonly reported events related to the drug
 - Reversible corneal epitheliopathy
- Rare and serious events related to the drug
 - Sterile endophthalmitis
- *Possible side effects and complications related to intravitreal injections are listed in section 7.4*

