7.3. Intravitreal ranibizumab

- Commonly reported events related to the drug
 - Mild visual disturbances
 - Transient IOP increase
- Rare and serious events related to the drug
 - Potential risk of arterial thromboembolic events (ATEs. i.e., nonfatal stroke, nonfatal myocardial infarction, or vascular death). However, the rates in the Lucentis clinical trials were low. In two studies for treatment of macular edema following retinal vein occlusion, the ATE rate at 6 months was 0.8% for both the subjects treated with intravitreal ranibizumab (0.3 mg or 0.5 mg) and the control group. In studies for treatment of diabetic macular edema the ATE rates at 2 years were: 7.2% for subjects treated with 0.5 mg; 5.6% for 0.3 mg and 5.2 for control. Stroke rates were 3.2%, 1.2% and 1.6%, respectively ¹²⁸. In a population based nested case-control

study intravitreal bevacizumab and ranibizumab were not associated with significant risk of ischemic stroke, acute myocardial infarction, congestive heart failure or venous thromboembolisms.¹²⁹

- *Possible side effects and complications related to intravitreal injections are listed in section 7.4*

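### Corneal epitheliopathy, the one drug event section 7.2 lists as common for methotrexate, is not a defined, separately compared safety outcome and rests on general unmasked AE reporting that can close too early

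*Combined protocol and SAP*

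**What the plan says.** Section 2.1 states that the trial is meant to "find out which intravitreal therapy offers the best balance of effectiveness and tolerability".

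Section 7 lists the known harms by drug. For methotrexate (7.2) the only entry under commonly reported drug events is "Reversible corneal epitheliopathy", and the only rare and serious entry is "Sterile endophthalmitis". For dexamethasone (7.1) the common entry is "Elevated intraocular pressure (IOP) which may require medication to lower". For ranibizumab (7.3) the common entries include "Transient IOP increase".

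Section 3.5 makes IOP elevation a secondary outcome at three thresholds. It then lists safety outcomes: IOP again, followed by "vitreous hemorrhage; retinal tear/detachment; endophthalmitis; severe vision loss". No corneal event is named there, in the abstract's adverse-event outcome (cataract and IOP elevation), or among the events of special interest in 8.4.10, which are for Lucentis only.

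The background (1.6) describes a six-month pilot study of a single intravitreal methotrexate injection: "The only evident treatment related side effect was corneal epitheliopathy in one patient", seen two months after the first injection.

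The general AE provisions are these:

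- 8.3.2 asks for all AEs, including those found on examination.
- 8.3.1 ends the mandatory period 30 days after the last study treatment, or at discontinuation or termination if that comes first. After that, only SAEs attributed to prior treatment are to be reported.
- 3.8 marks AE monitoring and an ophthalmic exam at every visit from M01 to M07 (week 24).
- 9.2 compares AE rates with a negative binomial model.

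**The concern.** When tolerability is half of the objective, each drug's known common harm should be measured in the same way in every arm. For dexamethasone this is done: IOP is measured at every visit and analysed at fixed thresholds. For methotrexate, the corresponding event depends on a clinician noticing it, deciding that it is an AE and reporting it while the reporting period is open.

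Two features weaken that route. Treating physicians and patients are unmasked (3.1), and the methotrexate clinician knows which event to expect. Also, 8.2.1 describes safety assessment in terms of treatment-related events, whereas 8.3.2 asks for all events and counts a known pattern of response towards a judgment of relatedness. The same corneal finding could therefore be handled differently in different arms. That is an inference from the rules, not something the protocol states.

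At stake is whether the report can give a comparable frequency of this event by arm. The primary efficacy result is not affected. The revision history for version 1.6 says 3.5 was revised to reflect the outcomes planned for the primary-results manuscript, so absence from that list matters for what readers will see.

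**Working it through.** The plan gives no figure for this event, so there is none to reproduce. The check has two parts.

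**1. Can the reporting window miss the event?**

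Inputs: close at last injection + 30 days (8.3.1); visits at weeks 0, 4 and 8 (4.2.1); event two months, about 60 days, after injection (1.6); end of follow-up at week 24, day 168 (3.8). Assume injections on nominal visit days, the first on the day of randomization, and no treatment at M04 or later.

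| Last study injection | Who | Day | Window closes |
|---|---|---|---|
| M01 | methotrexate or dexamethasone patients not retreated | 0 | 0 + 30 = day 30 |
| M02 | methotrexate patients retreated only at week 4 | 28 | 28 + 30 = day 58 |
| M03 | all ranibizumab patients on schedule; others retreated at week 8 | 56 | 56 + 30 = day 86 |

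A non-serious event 60 days after the last injection is outside the window in every row, because 60 > 30. For a methotrexate patient injected once, mandatory reporting stops at day 30, leaving 168 − 30 = 138 days of scheduled follow-up uncovered by 8.3.1, although 3.8 still marks AE monitoring. Scheduled ranibizumab patients stay in the window to about week 12. Observation time thus differs by arm and, because methotrexate retreatment depends on the OCT findings, by response. A site following 3.8 would record the pilot-type case; a site following 8.3.1 need not.

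**2. How many events might there be?**

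Inputs: 1 case; 15 patients (the denominator in 1.6); 80 patients per arm (3.1).

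- Rate: 1/15 = 6.7%.
- Exact (Clopper-Pearson) 95% limits: lower 1 − 0.975^(1/15) = 0.0017; upper solves (1 − p)^15 + 15p(1 − p)^14 = 0.025, giving p = 0.319.
- Expected in 80 patients: 80 × 0.0667 = 5.3. At the limits, 80 × 0.0017 = 0.1 and 80 × 0.319 = 25.5.

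The pilot concerned a single injection. Here methotrexate is required at M01, and at M02 and M03 if retreatment criteria are met, so up to three injections can be required by week 8. The rate in this trial could differ.

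To show what a named comparison could detect, assume a 1% rate in the comparator (not a document figure), 80 per arm and two-sided 0.05:

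power = Φ{[(p₁ − p₂) − 1.96√(2p̄(1 − p̄)/n)] / √([p₁(1 − p₁) + p₂(1 − p₂)]/n)}

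| Methotrexate rate | Expected of 80 | Power |
|---|---|---|
| 6.7% | 5 | 46% |
| 10% | 8 | 71% |
| 20% | 16 | 98% |

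This is a normal approximation with under one expected comparator event (80 × 0.01 = 0.8). An exact test would have less power at the low rates.

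**The case against.** The strongest reply is that the event is already covered. The list in 3.5 is open: "Safety outcomes including elevated IOP (>30 mm Hg thresholds); vitreous hemorrhage; retinal tear/detachment; endophthalmitis; severe vision loss". All AEs are to be reported, one visit schedule applies to all arms, 8.4.1 asks for a consistent way of eliciting AEs, 9.2 compares AE rates, and the DSMC sees AE data compared by assignment (11.2). A reader might infer that no safety outcome could count epitheliopathy. These provisions show that to be too strong, and that part of the reply stands.

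Three other inferences also go too far:

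- *Methotrexate's harms are left out altogether.* Endophthalmitis is named in 3.5 and is not limited to infectious cases, so sterile cases may count.
- *The list tilts one way, towards methotrexate.* IOP elevation is also a listed ranibizumab and injection event (7.3, 7.4), and cataract, a listed dexamethasone event, is absent from 3.5 as well.
- *Epitheliopathy would depress acuity.* The documents do not say so, and 7.2 calls it reversible.

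It is also fair that the detailed AE instructions are in the Manual of Procedures, which is not among the documents, and that the evidence is a single case.

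What the reply does not supply is a definition, a comparison specific to this event, or a window that reaches it. The AE elicitation examples in 8.4.1 are non-directive questions, an overall AE rate does not isolate one event type, and 8.3.1 can close before an event with the pilot's timing.

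**Conclusion.** The point holds as a gap in pre-specification. Section 3.5 does not define corneal epitheliopathy or compare it separately, and the general reporting route on which it relies is unmasked and has a window that conflicts with 3.8. In a methotrexate patient treated once, a case with the pilot's timing falls about 30 days (60 − 30) after mandatory reporting ends.

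The size is uncertain: about 5 of 80 methotrexate patients at the pilot rate, with a range from almost none to about 25. At the pilot rate a formal comparison would probably be inconclusive (about 46% power against an assumed 1%). At 20% it would be clear.

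The conclusion assumes that the Manual of Procedures does not already provide a corneal form item with its own definition and a longer window. It does not extend to any claim about the direction of the trial's overall tolerability conclusion.

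**What to change.** 1. Add to the safety outcomes in 3.5: *new or worsened corneal epitheliopathy in a study eye at any scheduled visit through week 24*, with a one-line definition common to all arms, agreed by the investigators.
2. Record status at M01, because exclusion criterion 3 allows a history of keratitis due to dry eye and new findings must be separable from old.
3. Record it present or absent on the same form item in all three arms at the ophthalmic exam already scheduled, regardless of attribution or time since the last injection.
4. In 9.2, compare the proportion of patients with the event as assigned, counting a patient with two study eyes once.
5. Reconcile the AE reporting period in 8.3.1 with the monitoring schedule in 3.8.

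The cost is one form item and one outcome line. No new procedure is needed if the scheduled ophthalmic exam includes the cornea, which 3.8 does not spell out. Sample size and primary analysis are unchanged. Two limits remain: the examiner is still unmasked, and precision will be low if the true rate is near the pilot's, so the result should be reported as an estimate with its interval.
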